**Figure 7 Study Design**

The visits during the study are planned as below:

- Screening visit: 12 weeks (90 days)
- 16 weeks treatment period:
  - Treatment Visit 1 (Week 1 [Day 1])
  - Treatment Visit 2 (Week 2 [Day 14 ± 3 days])
  - Treatment Visit 3 (Week 4 [Day 28 ± 3 days])
  - Treatment Visit 4 (Week 6 [Day 42 ± 3 days])
  - Treatment Visit 5 (Week 8 [Day 56 ± 3 days])
  - Treatment Visit 6 (Week 10 [Day 70 ± 3 days])
  - Treatment Visit 7 (Week 12 [Day 84 ± 3 days])
  - Treatment Visit 8 (Week 14 [Day 98 ± 3 days])
  - Treatment Visit 9 (Week 16 [Day 112 ± 3 days])
- 24 weeks safety follow-up period:
  - Follow-up Visit 1 (Week 20 [Day 140 ± 7 days])
  - Follow-up Visit 2 (Week 28 [Day 196 ± 7 days])
  - Follow-up Visit 3 (Week 40 [Day 280 ± 7 days])

Note: during follow-up patients are kept on NA until the end of the trial: Week 40

- (consolidation Phase).
- Post study consolidation period: after Week 40, the investigator can continue or stop NA therapy provided the following recommended plan is respected at the end of the study: after cessation of antiviral therapy, there is a transition of HBV care to a local provider for continued monitoring every 3 months with clinical and ALT/AST assessments for at least one year to monitor eventual HBV flares.

Please refer to [Section 6](#) for planned assessments/activities at each study visit.

Safety, tolerance, PK /PD and efficacy of EYP001a will be established in an outpatient setting. An external, independent Data Safety Monitoring Committee (DSMC) will review all available unblinded preliminary virology, safety, PK and PD results when any stopping rules ([Section 4.6](#)) are met in two or more subjects and on two occasions for a scheduled interim analysis. Please refer to [Section 3.3](#) for details.

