#### **6.2.4. Early Termination (ET) Visit**

The ET Visit is planned for patients who discontinue early from the study for any reason, for a follow-up approximately one week after administration of their final last dose of any study medication, regardless of how many days the patient was in the study. Please refer [Section 19.1](#) for the collection of data based on the following activities planned for the visit:

- Review and record patient's prior and concomitant medications
- Record patient's body weight
- Calculate BMI
- Perform symptom-directed physical examination
- Perform vital signs (systolic/diastolic BP, heart rate, temperature, respiratory rate)
- Pruritus assessment
- AE monitoring
- Perform clinical laboratory analysis including haematology, serum chemistry panel, coagulation tests and lipid and metabolic profile
- Perform serum pregnancy test (for WOCBP only)
- Perform Dipstick urinalysis for all male and female patients
- Perform 12-Lead ECG
- Sampling for analysis of HBV response markers
- PD biomarker sampling
- Liver fibrosis and inflammation assessment
- Perform Fibroscan VCTE
- PK sampling
- Review returned patient diary
- Collect used/unused study drug and assess compliance

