2. PROJECT OVERVIEW

2.1 Study Design

This is a prospective, multi-centre, international randomized, double-blind, placebo controlled, Phase 2a experimental study of oral FXR modulator EYP001a/placebo combined with Nucleos(t)ide analogues (NA) in virologically suppressed CHB patients to improve functional cure rates.

In total 49 eligible patients will be enrolled and randomized at approximately 14 study sites in 4 countries. Patients will be randomized prior to study drug (EYP001a or placebo and NA) administration on Day 1 in the ratio of 3:1 into 2 arms:

[figure not shown]
- Experimental Arm: EYP001a 200 mg once daily (QD) + NA daily (37 patients)
- Control Arm: Placebo + NA daily (12 patients)

Patients will also be stratified per HBeAg status, based on medical history HBeAg value or established during screening, to obtain a balanced randomization to both study arms.

The maximum total engagement duration for eligible patients in this study is up to 370 days: 90 days screening, 112 days (16 weeks) experimental treatment period and 168 days (24 weeks) follow-up on NA standard of care therapy (SOC) only.

Patients enrolled in the study will be assessed as outpatients. Patient screening will occur no more than 90 days prior to the Day 1 visit. Eligible patients will undergo further assessments on Day 1 to qualify for study drug administration on Day 1.

Figure 1: Study Design

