4.1.6 Per Protocol (PP) Analysis Set

The PP set is defined as the set of patients who meet the mITT set requirements and were not associated with a major protocol violation. This set will be identified before the start of the final analysis and will be used to support the analysis conducted for the primary efficacy endpoint. Patients will be analyzed based on the actual treatment received and patients with the study drug compliance of <50% will be excluded.

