8. TREATMENT EXPOSURE AND COMPLIANCE

EYP001a/Placebo administration information (study drug administered (Yes/No), reason for non-administration date and time of administration, reason for dose adjustment and adjusted dose administered will be listed by treatment group. Patient fasting listed will also be noted.

For NA, treatment administered, reason not administered, date and time of administration, dose taken per protocol (Yes/No), reason for dose adjustment and adjusted dose administered will be listed by treatment group. NA switching during the screening period will also be listed.

Missed doses and reason for missed doses along with corresponding AEs will be listed as well.

EYP001a/Placebo and NA accountability will be listed by treatment group. The following fields will be included: number of 200mg tablets dispensed, date dispensed, number of 200mg tablets used, date returned, doses missed (Yes/No), patient compliant (Yes/No), if no reason not compliant and the percentage of treatment compliance.

Treatment Compliance is defined as:

$$\left(\frac{\text{Total Drug Administered}}{\text{Expected Drug Administered}} \right) * 100$$

The total drug administered is defined as:

(Number of 200mg Tablets Used + Number of NA Tablets Used during treatment period)

The expected drug administered is defined as:

The expected drug administered for EYP001a/Placebo + The expected drug administered for NA during treatment period

- The expected drug administered for EYP001a/Placebo is defined as:

Number of treatment days for EYP001a/Placebo × daily dosage (= 1 tablet), where the number of treatment days for EYP001a/Placebo will be calculated as:

Number of treatment Day = (Date of treatment visit 1 - Date of last treatment visit) +1 during treatment period.

- The expected drug administered for NA is defined as:

Number of treatment days for NA × daily dosage (= 1 tablet), where the number of treatment days for NA will be calculated as:

Number of treatment Day = (Date of treatment visit 1 - Date of last treatment visit) +1 during treatment period.

Treatment compliance (including count and percentage with <50% compliance, >=50% and =< 80%, and > 80% compliance) will be summarized descriptively as described in section 3.1(categorical descriptive analysis) under Safety analysis set.

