SD: Standard Deviation. Percentages are calculated (the denominator used for the calculation) based on the number of participants in the ITT Set in each treatment group (N).

*For PCR-based Quantitative HCV Viral Load, percentages are based on the number of anti-HCV positive participants.

Programming note:

- Repeat for table 14.1.3.2 (mITT Set), table 14.1.3.3 (Safety Set) and table 14.1.3.4 (PP Set)

Table 14.1.4 Summary of Treatment Compliance (Safety set)

Category	Group 1 (N=xx)	etc.	Group x (N=xx)
n	xx	xx	xx
< 50% Compliance	xx (xx.x%)	xx (xx.x%)	xx (xx.x%)
>= 50% and =< 80% Compliance	xx (xx.x%)	xx (xx.x%)	xx (xx.x%)
> 80% Compliance	xx (xx.x%)	xx (xx.x%)	xx (xx.x%)

Source Listing: 16.2.5.2, 16.2.5.3

Table 14.2.1.1.x Summary of HBsAg by A Genotype (ITT Set)

Genotype: A

Visit Statistics	Group 1 (N=XXX)		etc.		Group x (N=XXX)	
	Actual Value	Change from Baseline	Actual Value	Change from Baseline	Actual Value	Change from Baseline
Baseline [1]						
N	XX	N/A	XX	N/A	XX	N/A
Mean	XX	N/A	XX	N/A	XX	N/A
SD	XX	N/A	XX	N/A	XX	N/A
Median	XX	N/A	XX	N/A	XX	N/A
Minimum	XX	N/A	XX	N/A	XX	N/A
Maximum	XX	N/A	XX	N/A	XX	N/A
Week 2						
N	XX	XX	XX	XX	XX	XX
Mean	XX	XX	XX	XX	XX	XX
SD	XX	XX	XX	XX	XX	XX
Median	XX	XX	XX	XX	XX	XX
Minimum	XX	XX	XX	XX	XX	XX
Maximum	XX	XX	XX	XX	XX	XX
Week xx						
n	XX	XX	XX	XX	XX	XX
Mean	XX	XX	XX	XX	XX	XX
SD	XX	XX	XX	XX	XX	XX
Median	XX	XX	XX	XX	XX	XX
Minimum	XX	XX	XX	XX	XX	XX
Maximum	XX	XX	XX	XX	XX	XX

Source Listing: 16.2.6.1

SD: Standard Deviation. N/A = Not Applicable.

[1] Baseline is defined as the average of screening and day 1 pre-dose.

Programming Note:

- Repeat for Genotype: Non A

- Repeat for table 14.2.1.1.2 (ITT set with no imputation), 14.2.1.2.1 (mITT with imputation), 14.2.1.2.2 (mITT with no imputation), 14.2.1.3.1 (PP set with imputation) and 14.2.1.3.2 (PP set with no imputation).

Table 14.2.2.x Analysis of HBsAg: Baseline to Week 16 (ITT Set)

	EYP001a 200 mg QD + NA daily (N=XXX)	Placebo + NA daily (N=XXX)
Week 2		
n	XX	XX
Mean change from baseline	XX	XX
LS Mean change from baseline	XX	XX
95% CI on LS mean change from baseline	XX,XX	XX,XX
SE on LS mean change from baseline	xx.xx	xx.xx
p-value	.xxx	.xxx
Difference in change from baseline at Week 10		
N	XX	
Mean	XX	
LS Mean	XX,XX	
95% on LS Mean	XX,XX	
SE on LS Mean	xx.xx	
p-value	.xxx	
<Repeat for Week 4,6,8,10,12,14,16>		

Source Listing: 16.2.6.1

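### SAP 8 subtracts the treatment dates in the wrong order, so full adherence scores -102%; with the sign corrected, the count still gives adherent early leavers about 100%

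*SAP*

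**What the plan says.** SAP 8 defines compliance as total drug administered over expected drug administered, times 100. The numerator is "Number of 200mg Tablets Used + Number of NA Tablets Used during treatment period". The denominator adds an expected count for each product, each being treatment days times one tablet a day. In both lines the treatment days are "Number of treatment Day = (Date of treatment visit 1 - Date of last treatment visit) +1 during treatment period".

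The percentage has two uses:

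- SAP 4.1.6 adds a compliance condition to the PP set: "patients with the study drug compliance of <50% will be excluded".
- SAP 8 and mock Table 14.1.4 summarise it on the Safety set in three bands, the top one being "> 80% Compliance". The table list in SAP 18 marks Table 14.1.4 for both DSMC meetings.

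SAP 2.1 gives the planned length as "112 days (16 weeks) experimental treatment period". Protocol 6.2.4 places the early termination visit "approximately one week after administration of their final last dose of any study medication", outside the numbered treatment visits. SAP 3.2 counts study days as the event date minus the first-dose date, plus 1.

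**The concern.** There are two separate faults in the denominator.

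First, the earlier date has the later date subtracted from it, so expected tablets are negative for anyone followed beyond the first days. A negative percentage is below 50%, and the 50% rule decides who enters the PP set. That set supports the primary endpoint through Tables 14.2.2.3.1 and 14.2.2.3.2.

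Second, the count ends at the last treatment visit, and the SAP does not say which date that is for a patient who never reaches Week 16. The natural reading is the last one attended. Leaving the study then shortens the expected course along with the actual one, so attendance sets the band as much as tablets taken. What is at stake here is the meaning of Table 14.1.4.

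**Working it through.** **Inputs.** One tablet a day of each product (SAP 8); planned course 112 days (SAP 2.1); Week 16 visit on Day 112, window ±3 days (Protocol 3.1); first dose on Day 1 (SAP 3.2). Let L be the study day of the last treatment visit.

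**Formulas.** As written: days = (1 - L) + 1. Sign corrected: days = (L - 1) + 1. Compliance = 100 × (EYP001a/placebo tablets + NA tablets) / (2 × days).

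**The plan's own figure.** The SAP states no compliance percentage, so the only figure to reproduce is the 112-day course. As written, (1 - 112) + 1 = -110, which does not reproduce it. Sign corrected, (112 - 1) + 1 = 112, which does.

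**Completers, formula as written.**

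- Every tablet taken, L = 112: (112 + 112) / (-110 - 110) = 224/(-220) = -101.8%.
- Across the visit window: -101.9% at Day 109 and -101.8% at Day 115.
- Half the tablets taken, L = 112: 112/(-220) = -50.9%.

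Any completer who took at least one tablet has a negative value, hence one below 50%. The formula gives zero days (division by zero) at L = 2 and a positive count only at L = 1.

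**Early leavers, sign corrected.** Take a patient who takes both products daily to the last treatment visit and then leaves.

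| Last treatment visit | Compliance, sign corrected | Share of planned 112 days |
|---|---|---|
| Day 14 | 100% | 12.5% |
| Day 28 | 100% | 25% |
| Day 42 | 100% | 37.5% |
| Day 56 | 100% | 50% |
| Day 84 | 100% | 75% |
| Day 98 | 100% | 87.5% |

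All six fall in the top band of Table 14.1.4. Against the planned course, only the Day 98 leaver would. Dosing for 7 days past a Day 28 visit gives 35/28 = 125%. A leaver who took half the doses up to that visit gets 50%, so the 100% depends on adherence while on study.

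**Same EYP001a exposure, different attendance.** Both patients take 28 EYP001a/placebo tablets, 28/112 = 25% of plan.

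- Leaves at Day 28: (28 + 28)/(28 + 28) = 100%, top band.
- Stops EYP001a/placebo at Day 28 but attends to Week 16 with full NA: (28 + 112)/(112 + 112) = 62.5%, middle band.

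Over the planned period the leaver would score (28 + 28)/224 = 25%, and the patient who stays would remain at 62.5%. The difference that remains reflects NA tablets taken on study, because SAP 8 pools the two products. That is a separate matter.

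**Reach into the PP set.** PP membership requires mITT membership (SAP 4.1.6), and mITT requires a 16-week assessment (SAP 4.1.2). A Week 4 leaver is therefore already out of PP. For a patient who attends Week 16, the last treatment visit is Visit 9.

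**The case against.** The strongest reply is that the reversed dates are a slip. SAP 3.2 has the right order, and a program returning about -102% for every adherent completer would be caught on its first run. That is fair as a forecast: a reader might infer that the trial will end up with no PP set, and the documents do not support that. What stands is that the written rule is wrong in two places and decides membership of an analysis set. Correcting it silently in code would be an unrecorded departure from the SAP.

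A second reply is that compliance while on study is a legitimate measure and that persistence belongs in the disposition tables. This also has force. However, SAP 8 neither labels its figure as on-treatment nor uses dose dates. It uses a visit date, which can give more than 100% and treats two patients with the same EYP001a exposure differently.

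Three stronger readings should be resisted:

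- **That the early-leaver effect distorts the PP set.** The mITT requirement largely prevents this.
- **That the DSMC would be misled about drug delivery.** Both reviews also receive Table 14.1.1 (disposition with reasons), Table 14.3.3.6 (adverse events leading to discontinuation) and Listing 16.2.7.3. The second adds the exposure and missed-dose listings, 16.2.5.2 and 16.2.5.4.
- **That a number of misclassified patients can be projected from EYP001-202.** Protocol 5.4 reports five pruritus episodes leading to early treatment termination among 24 NASH subjects, pooled over three regimens and placebo. Those are episodes, and ending treatment is not the same as leaving the study. SAP 15 also records that enrolment was suspended after about 25 randomizations.

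**Conclusion.** Both faults are real, and they differ in kind.

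The date reversal is an arithmetic error. It gives -110 expected tablets per product and -102% for full adherence, and on a literal reading the 50% rule removes every completer who took study drug. This needs only the SAP's own formula and a Day 112 visit.

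The end-date fault is an incomplete definition. With the sign corrected, it gives 100% to a patient who took 25% of the planned course and left, against 62.5% for one with the same EYP001a exposure who stayed with full NA. This assumes that the last treatment visit means the last one attended, that the early termination visit is not a treatment visit, and that the leaver was adherent until then. Its effect is on Table 14.1.4 and is not material to the PP set. The documents do not allow the number of affected patients to be estimated.

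**What to change.** In SAP 8:

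1. In **both** lines (EYP001a/placebo and NA), define treatment days as (date of last treatment visit - date of Visit 1) + 1. Correcting one line only would leave a completer with a summed denominator of 112 + (-110) = 2.
2. State the end date: the Week 16 visit for patients who attend it; 112 planned days for patients who stopped or left before it and do not attend it; and, at a DSMC data cut, the last treatment visit on or before the cut for patients still on treatment. Count tablets used over the same period.
3. In Table 14.1.4, show the planned-period figure and an on-treatment figure, with days as (last dose date - first dose date) + 1, under separate labels.
4. In SAP 4.1.6, state which of the two the 50% rule uses.

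The cost is SAP wording and one derived variable. No new data are needed: SAP 5.1.1 already lists the last dose date. Reported compliance may look less favourable.

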9. PRIOR AND CONCOMITANT MEDICATIONS

Concomitant medications will be summarized by Anatomical Therapeutic Chemical (ATC) class Level 3 and PT as noted in section 3.1 (categorical descriptive analysis) using Safety analysis set. Participant who used the same medication on multiple occasions will only be counted once in the specific category (PT). PTs will be sorted alphabetically. In addition to the summaries by the coded terms, the number of participants who used at least one concomitant medication during the study will be presented.

Prior and concomitant medications will be presented in the by-participant data listings using Safety analysis set.

10. PHARMACOKINETICS

The PK analysis falls outside the scope of this SAP.

11. PHARMACODYNAMICS

All pharmacodynamic analysis will be based on the PD analysis Set.

The following PD endpoints will be analyzed:

- Plasma C4 (7 α -hydroxy-4-cholesten-3-one)
- FGF19
- Plasma primary and secondary BAs (optional)

PD endpoints will be summarized descriptively as described in section 3.1 (continuous descriptive analysis).

12. EFFICACY

All Efficacy analyses will be based on the ITT analysis set unless otherwise specified.

The following Efficacy endpoints will be analyzed:

- HBsAg decline ($\Delta \log_{10}$) from Baseline (screen and Day 1 average) to Week 16 of treatment.
- HBsAg responder rate (decrease from baseline ≥ 1.0 on the \log_{10} scale) at Week 16 of treatment and Weeks 20, 28 and 40 of follow up.
- HBsAg responder rate (decrease from baseline ≥ 0.5 on the \log_{10} scale) at Weeks 12 and 16 of treatment and Weeks 20, 28 and 40 of follow up.
- HBsAg loss rate (% patients with HBsAg < Lower Limit of Quantification (LLOQ)/TND) at Week 16 of treatment and Weeks 20, 28 and 40 of follow-up.
- HBsAg loss rate (Proportion of results that are Target Not Detected versus Target Detected) at Week 16 of treatment and Weeks 20, 28 and 40 of follow-up.
- Relapse rate HBsAg (% patients who became negative [HBsAg < LLOQ], then increased with HBsAg > LLOQ) at Week 16 of treatment period and Weeks 20, 28 and 40 during follow-up period.
- Virologic failure rate (breakthrough) of Hepatitis B virus Deoxyribonucleic Acid (HBV-DNA) (% patients with a confirmed quantifiable HBV DNA increase of $\geq 1\log_{10}$ HBV DNA copies/mL above LLOQ) assessed at Week 16 of treatment period and Weeks 20, 28 and 40 during follow-up period.
- HBV-pgRNA decline ($\Delta \log_{10}$) from Day 1 to Weeks 4, 8, 12, 16 of treatment period and Week 40 of maintenance period.
- HBcrAg decline ($\Delta \log_{10}$) from Day 1 to Weeks 4, 8, 12, 16 of treatment period and Week 40 of maintenance period.
- HBeAg quantification for HBeAg pos patients and changes at Week 16 of treatment and Week 40 of follow-up.
- Fibroscan Vibration Controlled Transient Elastography (VCTE) change from screening value to Weeks 16 and 40 or Early Termination (ET) value.
- Anti-HBs: Percent of subjects detectable (reactive) for Anti-HBs at baseline, Week 16 of treatment and Week40 of follow-up
- Anti-HBe: Percent of subjects detectable (reactive) for Anti-HBe at baseline, Week 16 of treatment and Week40 of follow-up

Efficacy endpoints at each scheduled visit will be summarized descriptively as described in section 3.1 (categorical descriptive analysis). All HBV response marker data collected at scheduled and unscheduled visits will be included in the listings.

For HBsAg, and HBV DNA, box plots for actual value and change from baseline value over time by treatment group, by HBeAg (positive and negative) and by A Genotype (yes and no) will be generated separately. Also, series plots for individual actual value over time and in change from baseline by HBeAg and by A genotype will be generated separately.

Furthermore, HBsAg, HBV-pgRNA, HBcrAg, HBeAg quantification for HBeAg pos patients and Fibroscan Vibration Controlled Transient Elastography (VCTE) at each scheduled visit and change from baseline values will be summarized descriptively as described in section 3.1 (continuous descriptive analysis). Counts (%) of number participants with Anti-HBs and Anti-HBe results at baseline, week 16 and week40 will also be presented (categorical descriptive analysis).

12.1 Inferential Analyses

The following endpoints will be analyzed as described in sections 3.3:

- HBsAg decline ($\Delta \log_{10}$) from Day 1 to Week 16 of treatment
- HBsAg responder rate (decrease from baseline ≥ 1.0 on the \log_{10} scale) at Week 16 of treatment and Week 40 of follow up. (secondary)
- HBsAg responder rate (decrease from baseline ≥ 0.5 on the \log_{10} scale) at Weeks 16 of treatment and Week 40 of follow up.
- HBsAg loss rate (% patients with HBsAg < Lower Limit of Quantification (LLOQ)/TND) at Week 16 of treatment and Week 40 of follow-up.
- HBsAg loss rate (% patients with HBsAg < Lower Limit of Quantification (LLOQ)/TD) at Week 16 of treatment and Week 40 of follow-up.

12.2 Other Analyses

ENYO is developing a mathematical computational HBV disease model. The results from EYP001-201 will serve as clinical data for the calibration of in silico HBV patients simulating the effect of combinational treatments that will eventually support designing later trials. With its different sub-models (HBV replication and excretion, BAs metabolism, cholesterol metabolism, immune system, fibrosis, blood virus related changes, and EYP001a, ETV and PEG-IFN α 2a drug models) the disease model of chronic HBV infection will be used to predict quantitative efficacy on relevant endpoints (DNA HBV in blood, HBsAg) in a representative virtual population. The computational model is a system of ordinary differential equations (ODEs) which integrates more than 300 biological variables and more than 1000 parameters. It will be used to explore the effect of combinations of different treatments regimens including EYP001a, ETV and PEG-IFN α 2a. Iterations of the validated model will serve for the exploration of alternative arms in future trials and in the EYP001-203 study (conducted in parallel EYP001-201, with treatment naive or virologically non-suppressed patients treated with EYP001a combined with NA and peg-IFN), by simulating different doses and treatment regimens. Disease model simulations will support future explorations of development strategies, with the upcoming EYP001a pivotal study designs.

This analysis is reported in a separate analysis plan (reference : Validation protocol HBV EYP001 modeling and simulation project) falls outside the scope of the SAP.

